The Study Guide Trial 2017: The Study Guide Cluster Randomized Control Trial

NCT03312218

MARCH 2017

Each year, over 1,200 residents challenge the Family Medicine certification exam. Scores obtained by candidates on national licensing exams are positively associated with the quality of patient care provided in future practice.¹⁻⁵ Therefore, educational methods to optimize residency training are vitally important.

This research is needed to improve residency training. Our objective is to deliver a trial-validated mobile application as a tool for improving the knowledge of future physicians. Through this definitive trial, we can advance residency training for thousands of physicians, for years to come.

Background

As a guide for residents preparing for their certification exam, the College of Family Physicians of Canada (CFPC) elaborated the concept of Priority Topics.⁶ A major challenge for residents is knowledge retention.^{7,8} To address this challenge, the strategy of spaced education emerged from research in educational psychology.⁹ Spaced education takes advantage of (1) the spacing effect and (2) the testing effect.^{10,11} With the *spacing effect*, students can increase their retention of information by interval rereading of content. The *testing effect* refers to the following: when combined with answer feedback, the process of testing one's knowledge alters learning itself, to improve recall.¹²⁻¹⁵ Greater resident engagement in self-learning is needed to implement spaced education. In this context, it is critical to test interventions to enhance such engagement. Building on the findings of our prior CIHR-funded research and a pilot study, this proposal is grounded in a 'qualitative knowing' of the context of residency training in Family Medicine.¹⁶

Literature: Randomized controlled trials demonstrate that spaced education can boost long-term knowledge retention among students and residents in Urology.¹⁷⁻²¹ Outside of Urology, we found four small single-site trials of spaced education in residency (General Surgery, Oncology, Internal Medicine and Pediatrics).²²⁻²⁵ We found no published studies of spaced education in the context of Family Medicine. Guided by a specialized librarian, our searches were conducted iteratively in Google Scholar and three databases - PubMed, EMBASE, and ERIC. We provide our search strategies, and a summary of findings table, in the appendix.

Importance

This research is important for five reasons. (1) Foundational knowledge guides decision-making in practice; yet the Canadian family medicine residency is the shortest among developed nations, at just two years. (2) The implementation of work hour restrictions has reduced the time for learning in group settings. While the time to teach in residency may never be sufficient to master the body of knowledge required for practice, the importance of foundational knowledge is supported by observational studies showing correlations between certification exam scores (competence) and performance in actual practice. Please see the appendix for a definition of these terms. For example, Tamblyn et al. reported that family medicine residents achieving higher scores on their certification exam were more likely as family physicians in their early years of practice to prescribe fewer contraindicated drugs. Initial assessment of these outcomes was limited to the first 18 months of practice. Subsequently, Tamblyn et al. reported a sustained positive relationship between certification exam scores and performance over 4 to 7 years in practice.^{3,4} While observational studies like these do not allow for causal inference, interventions to improve the knowledge of future family physicians should improve health care for Canadians, given the importance of primary care to health systems.²⁶ (3) Although residency training in Family Medicine does not yet leverage the benefit of spaced education, our pilot study reveals the feasibility of using a mobile app to implement this instructional approach. In line with our conceptual framework²⁷, in a manuscript under review and in conference presentations we have reported that alerts from a mobile app stimulate residents to read exam-relevant clinical information. In this pilot study, we offered an app on the 99 Priority Topics to first-year residents at McGill and McMaster. Respectively, 93% and 84% of all incoming residents were consented.²⁸ Through the app, McMaster residents received a weekly alert to one

priority topic. McGill residents were given the same app but received no alerts, providing them with information on demand. After 100 days, we performed an interim analysis on the number of opened pages in the app, using priority topics as pairs. Intervention group residents opened more pages of information, per priority topic (15.7 ± 21.8 vs 9.1 ± 14.4 , $p < 0.0003$). These findings are promising. (4) There are no studies of spaced education in the context of Family Medicine training. (5) Our ability to conduct the proposed work is enhanced through a partnership with the CFPC. Thus, our proposed research is feasible, innovative and supported by pilot study findings.

Research question

Among family medicine residents, does enhanced feedback through an app providing alerts and test questions (spaced education), compared to the same app without alerts and enhanced feedback (no spaced education), improve competence as measured by the certification examination?

Design: We propose a cluster randomized controlled trial. For this trial, a medical school is a natural cluster of residents, with no crossovers. This study will be registered at clinicaltrials.gov and conducted to the highest standards. To ensure good reporting, our main manuscript will include all essential elements in accordance with standards articulated in the CONSORT statement.²⁹ The trial will be coordinated by RG who will chair the steering committee comprised of co-applicants. Research assistants supervised by co-applicants and collaborators will manage the trial at each site. First-year residents will enter the trial in December 2017.

What are the planned trial interventions? We will take advantage of a popular commercial app containing 70 unique clinical cases with test questions that simulate the short answer problems on the certification examination. The FM Study Guide (hereafter the 'Study Guide') is a mobile device based platform for residents to test their knowledge of typical clinical cases covering Priority Topics in Family Medicine. Please see screenshots at <http://www.familymedicinestudyguide.com/>. Created in 2015 as a non-profit venture by co-applicant DL, 100% of app revenue is donated to charities or used to ensure app sustainability. Through the Study Guide, residents interact with test questions. These interactions can last 5 minutes or less, and therefore fit easily into the lives of busy residents. For this trial, we will modify the app to provide a weekly alert as well as adaptive reinforcement of content based on test question performance. This will allow intervention group residents to take full advantage of both the spacing and the testing effect. However, both versions of the app will provide equivalent cases and test questions to intervention and control groups.

Intervention: Immediately after consenting to participate, we will provide residents a coupon for a free copy of a modified version of the Study Guide. This will allow intervention group residents to access the modified app. Participants will then receive an *alert to the clinical case of the week* on their smartphone or tablet computer (iOS or Android). On tapping this alert, the app will open to allow reading of this case and up to 5 case-related test questions. As each question is answered, participants get immediate feedback by comparing their answer with the textbook answer provided on the subsequent screen. For each case, after the final question, participants will reflect on the correctness of their answers, using a checklist with two response options, as follows: (1) My answers are (largely) correct, or (2) My answers are (largely) incorrect. If incorrect, the adaptive system will automatically send an alert to that specific case in 7 days, to promote learning by repeating its questions. Correctly answered questions will also be re-presented to participants, but via an alert to repeat that case and its questions in 14 days. These spacing intervals between repetitions were based on research findings to optimize long-term retention of learning.¹⁰ Alerts to case-related questions will be retired (no longer sent) under two conditions: once the case and its questions are answered correctly twice consecutively, or by request after three attempts.

In the appendix, we provide an algorithm to summarize this intervention.

Comparison: Residents in the control group will receive the standard version of the app at no charge, with no alerts. This version will provide the equivalent of clinical cases and test questions-on-demand.

Participants in both groups will be encouraged to answer test questions, as each university will create an alias (avatar) for healthy competition. Each alias will earn one point for each attempt to answer a set of case-related questions. Total points earned per university will be displayed as scores on a leaderboard to encourage this competition.²⁰

What are the proposed arrangements for allocating participants to trial groups? One co-applicant (JK) will conduct a computer generated and blinded central randomization procedure of universities (clusters) to trial groups. As the unit of randomization, all Canadian universities will be stratified per the median number of residents by site, and then randomly allocated to the intervention or the control arm. This will minimize the effect of any inequality between clusters on the results. Following randomization, recruitment will begin locally as co-investigators at each site will obtain a list of their eligible residents. Consenting residents will then receive a coupon to install the app by the start date. The period from July to November 2017 will provide ample time to obtain consent. Participants will exit the study on the first day of their exam in the spring of 2019.

What are the proposed methods for protecting against sources of bias? Trial outcomes (exam scores and questions completed) are objectively assessed. Residents will be blinded to the nature of the intervention. Our consent form will not mention our research questions or the intervention. The certification exam will be scored by persons unaware of group allocation.

How will contamination be addressed? Participants will unlock the trial versions of the app using a coupon with a unique login number. We will track logins for each unique ID. With this tracking, intervention group residents will not access the version of the app destined for control group residents, or vice versa. In addition, randomization at geographically dispersed sites will limit the ability of intervention group residents to influence those allocated to the control group. Residents at different universities share no core rotations.

What are the planned inclusion/exclusion criteria? All incoming family medicine residents in Canada will be eligible. These eligible residents will be clustered within university training programs. We will exclude residents from other specialties who happen to be on rotation in Family Medicine. We will deliver the intervention from December 2017 to April 2019 (70 weeks). We will follow each resident and provide tech support.

What are the proposed primary and secondary outcome measures? Our primary outcome will be the score on the written component of the CFPC certification exam in April 2019. Co-applicant CB is authorized by the CFPC to provide de-identified scores for each participant. We will also test the hypothesis that alerts to reinforcement of content result in greater resident engagement with test questions, as compared with control residents not exposed to alerts to reinforcement of content. Therefore, our secondary outcome will be the number, percentage and time to completion of all correctly answered questions, per case. These data will help explain the expected improvement in exam scores.

Using a study “dashboard”, we will monitor app usage over time at the group level, by examining a dynamic count of answered questions. In addition to counting attempts and correctly answered questions, the date and time of each attempt will be tracked and automatically recorded at the server. Thus, for each

case and for each participant, we will calculate a time to completion of that case. This will be defined by counting the number of days from the study start date in 2017 to the date that test questions for that case were deemed to be correctly answered.

Through a baseline questionnaire, we will collect data on potential confounders at the participant level: age, sex, Canadian or International Medical Graduate status and whether they hold a graduate degree.

What is the proposed sample size and what is the justification for the assumptions underlying the power calculations? We will have 80% power to detect an effect size of 0.4 (Cohen's d). This effect corresponds to a 4% absolute increase in score, equivalent to two additional correct exam questions. Assumptions: Clusters will provide an average of 80 residents. Given this projected number, we will consent a minimum of $8 \times 80 = 640$ residents at 8 university training sites. If residents at 12 sites are consented, we will have adequate power to detect an effect size of 0.4. These assumptions are based on pilot study findings as well as actual scores obtained by all residents in Canada on the certification exams conducted in the spring of 2015 and the spring of 2016. We detail our calculation of the proposed sample size (and the design effect) in the appendix.

What is the planned recruitment rate? What evidence is there that the planned recruitment rate is achievable? With support from co-investigators and collaborators, each university will recruit at least 80% of their residents. The evidence for this comes from our pilot study, in which we consented more than 80% of residents at two university sites in Quebec and Ontario. This is not surprising; residents perceive a need for an app based on Priority Topics to help pass a high-stakes exam. We will report the number of residents eligible for participation in both study arms, their flow through the study and losses to follow up using a CONSORT-style flow diagram. While we anticipate a small loss of consenting residents to follow up, for example at McGill just two residents transfer out, on average per year.

What is the proposed type of analyses? We will follow the guidelines of the CONSORT statement for clustered randomized trials and recommendations for their analysis when presenting and analysing our data.²⁹ The primary efficacy analysis will be based on the intention-to-treat population i.e. all study participants will be analysed as randomized. The primary statistical analysis will evaluate the difference in mean exam scores between residents in the intervention and control groups using a linear mixed effects model. The mixed model will incorporate study site as a random factor and the following fixed factors (as presumed predictors of exam score): study group assignment (control / intervention), age, sex, completion of a graduate degree, and IMG status. The estimated fixed effects will be reported along with 95% confidence intervals. Confirmatory assessment of the primary endpoint will be based on the confidence interval for the fixed effect estimate of "study group", implying a two-sided level of significance (against the null hypothesis of no effect) of 0.05.

Regarding the secondary outcome of time to correct completion of test questions: For each resident, a mean time to event (with confidence intervals) will be calculated separately for each clinical case in the app, averaged and then compared across groups. These data will be described using a Kaplan-Meier curve. To account for clustering while adjusting for potential confounders, we will use a Cox regression model with a sandwich covariance structure. In the adjusted model, we will compare the hazard for this secondary outcome, between intervention and control groups, as of April 2019.

What is the process for ethics approval? We have already initiated the approval process. At McGill, the IRB policy is to complete the review of an approval request once funding has been secured. We provide a draft of our consent form in the appendix. Residents will be told we are tracking their attempts to

complete test questions. Note that co-investigators at each university site will liaise with local officials to obtain the necessary approvals following IRB approval at McGill.³⁰

The risks associated with resident participation in medical education research are not negligible, and could theoretically include: fatigue, stress, alteration of self-concept, and loss of confidence.³¹ We will take the following steps to mitigate such risks for residents who participate. First, regarding informed consent, residents may decline to participate; in so doing, we will clarify that residents can still purchase the Study Guide. This will reduce the risk of coercion to participate. Second, de-identified examination scores from the CFPC will be made available to the research team only after the residency has ended. Thus, there is no concern that resident participation *within* the study will affect a program director's evaluation of the resident *after* the study.

Expertise, Experience and Participatory Approach

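### A leaderboard that appears to be shared across arms is scored by attempts that only the intervention app prompts, giving a route of interference that the contamination section does not cover

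*Combined protocol and SAP*

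**What the plan says.** The Comparison paragraph, under the planned trial interventions, sets up the competition for both arms: "Participants in both groups will be encouraged to answer test questions, as each university will create an alias (avatar) for healthy competition". The scoring rule is "Each alias will earn one point for each attempt to answer a set of case-related questions", so repeats score and correctness does not. The display rule is "Total points earned per university will be displayed as scores on a leaderboard to encourage this competition". The board is in the singular, and no text divides it by arm or restricts who sees which scores.

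The Intervention paragraph describes repetition that only the intervention app prompts. After incorrect answers, "the adaptive system will automatically send an alert to that specific case in 7 days". After correct answers, "Correctly answered questions will also be re-presented to participants, but via an alert to repeat that case and its questions in 14 days". Alerts stop "once the case and its questions are answered correctly twice consecutively, or by request after three attempts". The control app has the equivalent cases and questions on demand, without alerts.

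The section on how contamination will be addressed relies on tracked logins, on the absence of shared core rotations, and on geographic dispersion, which "will limit the ability of intervention group residents to influence those allocated to the control group". It does not mention the leaderboard. The allocation section makes the university the unit of randomization, which is also the unit shown on the board.

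**The concern.** A leaderboard offered to both arms would be a neutral background if its content did not depend on allocation. Here it does. Points count attempts, and the intervention is a system for prompting further attempts. If control schools see those totals, what they see depends on the other arm's treatment, and the board exists to make residents react to it.

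The secondary hypothesis, that alerts increase engagement with test questions, is most directly exposed. The exam score is exposed only if the change in practice carries through to the written paper. A null result could then be hard to read, because it might reflect control schools catching up. A positive one could partly reflect control schools giving up. The planned mixed model, with site as a random factor, cannot separate either reaction from the treatment effect, because every control school would see the same kind of board.

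**Working it through.** **1. Is there a route between the arms?** Four statements, side by side:
- Both groups compete, by university (Comparison paragraph).
- Each attempt scores one point, and school totals are displayed (same paragraph).
- Repeat alerts go to the intervention arm only (Intervention and Comparison paragraphs).
- The safeguards are logins, dispersion and separate rotations (contamination section). Logins stop access to the wrong app version. Dispersion and rotations limit personal contact. None acts on a displayed score.

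If the board is common to both arms, the route exists and is not covered.

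**2. How large a gap could the scoring create?** Inputs: 70 cases (planned trial interventions), 80 residents per school (sample size section), and two attempts per case if each is answered correctly twice in a row.
- Intervention resident following every alert: 70 × 2 = 140 points.
- Control resident doing each case once: 70 × 1 = 70 points.
- Schools of 80: 80 × 140 = 11,200 against 80 × 70 = 5,600.

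This is an illustration, not a floor. Control residents may repeat cases at will and score each time. With one new case a week for 70 weeks, a 14-day repeat of the last case falls after the period ends. School size also matters: an intervention school with an assumed 40 residents would total 40 × 140 = 5,600, level with the control school of 80.

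The pilot gives indirect support for a gap: 15.7 pages opened per topic with alerts against 9.1 without, a ratio of 15.7 / 9.1 = 1.7. That counts page openings, not attempts.

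**3. The plan's power figure.** The plan states 80% power for d = 0.4 at two-sided 0.05. Without clustering, this needs 99 residents per arm. With clusters of 80, the design effect is 1 + 79 × ICC. The ICC is left to an appendix that is not in the supplied text, so the 80% cannot be reproduced. The ICC that would yield it is about 0.029 with 8 sites and 0.049 with 12 (normal approximation), or 0.016 and 0.038 (t distribution on 6 and 10 df).

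**4. What dilution would do, taking the 80% as given.** At 80% power the noncentrality is 1.96 + 0.84 = 2.80. If control schools take up a fraction f of the benefit, power = Φ(2.80 × (1 − f) − 1.96).

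| Assumed f | Effect d | Noncentrality | Power |
|---|---|---|---|
| 0 | 0.40 | 2.80 | 80% |
| 0.10 | 0.36 | 2.52 | 71% |
| 0.25 | 0.30 | 2.10 | 56% |

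The t version agrees within 1 percentage point for 8 or 12 sites. No value of f can be taken from the documents. Discouragement of control schools would move the contrast the other way.

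**The case against.** The strongest reply is that cross-arm visibility is inferred. The plan does not literally say that control residents see intervention schools' scores, and the arms use different app versions with separate logins. This stands as a limit on certainty. The singular board and the joint competition still make a shared display the natural reading, and one sentence from the sponsor would settle it.

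Second, the signal is noisy. Schools appear under aliases, residents are blinded to the nature of the intervention, some alias always leads, and raw totals also reflect school size and uptake. This stands against any claim that intervention schools must lead. It does not close the route, since a gap stays visible whoever is behind the alias.

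Third, a reader might infer that the leaderboard contradicts the contamination section. It does not: that section says dispersion will limit influence, not remove it. The section is incomplete.

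Fourth, the competition is a deliberate feature of both arms, and a common board gives both the same stimulus. With separate boards, intervention schools would see high-scoring rivals and control schools low-scoring ones, so the contrast would include each arm's own norm. This is a genuine cost of one form of the remedy and is carried into the fix.

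**Conclusion.** The concern holds as an uncovered route of interference, on the natural reading that one board shows schools from both arms. It does not hold as a demonstrated bias.

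A reader might infer that the planned contrast is certainly biased towards no effect, that intervention schools will score at least double, or that power will fall to 71% or 56%. The documents support none of these. They give no figure for any link from a visible gap, to extra attempts, to exam score. The direction is open, the 140 against 70 compares full adherence with one pass through the cases, and the power losses rest on assumed fractions and on the plan's unreproduced 80%.

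What remains is a cheap improvement worth making before launch. It serves the plan's own aim of limiting the influence of intervention residents on controls, and the effect could not readily be measured afterwards if every control school had seen the board.

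**What to change.** Before the December 2017 start:
- Filter the display so that no resident sees scores from the other arm. Use either one board per arm or competition within each university.
- Show points per consented resident instead of school totals, so that rank does not depend on school size.
- State in the contamination section who sees which scores, and that no cross-arm scores are shown before the April 2019 exam.

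The work is a server-side filter, a change of denominator and a sentence or two of protocol text.

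The costs differ by option. With 8 to 12 sites split evenly, a board per arm leaves 8 / 2 = 4 to 12 / 2 = 6 schools competing. Schools within an arm would still influence one another, so the contrast would include each arm's own competitive norm. Boards within each university avoid that but give up competition between schools. The sponsor should choose one and record the reason. If a common board is kept, the plan should acknowledge possible spillover in either direction as a limitation on interpreting both outcomes.

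### Universities are randomised within size strata, but the primary mixed model omits the stratum, and the protocol credits size stratification with more balance than it can give

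*Combined protocol and SAP*

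**What the plan says.** In the Protocol's section on allocating participants to trial groups, the university is the unit of randomisation and "all Canadian universities will be stratified per the median number of residents by site" before allocation to an arm. No other stratification factor is named. The next sentence claims: "This will minimize the effect of any inequality between clusters on the results".

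In the section on the type of analyses, the primary analysis is a linear mixed model: "The mixed model will incorporate study site as a random factor and the following fixed factors". The fixed factors are "study group assignment (control / intervention), age, sex, completion of a graduate degree, and IMG status". Neither the size stratum nor any other university-level term is listed. The covariates come from a baseline questionnaire through which "we will collect data on potential confounders at the participant level".

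The sample size section states: "We will have 80% power to detect an effect size of 0.4", and "This effect corresponds to a 4% absolute increase in score". It assumes 80 residents per university on average, with 8 universities as the minimum and 12 as the larger scenario. The ICC and design effect are left to an appendix that is not in the text supplied.

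**The concern.** Two things do not fit together.

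1. **The claim exceeds the method.** Splitting 8 to 12 universities at the median size can balance the arms on size. It gives no assurance on usual exam performance, case mix or teaching, except so far as these follow size.
2. **The design is stratified but the analysis is not.** Stratification stops any size effect from adding to the difference between arms. A model without the stratum leaves that size effect in the between-university residual, and so in the estimated standard error. The estimate gains from the stratification but the confidence interval does not.

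The primary conclusion rests on the confidence interval for study group. With 8 to 12 clusters, that interval is governed by between-university variance. If size matters, the trial could miss an effect it was built to detect.

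**Working it through.** **Inputs from the protocol.** d = 0.4 corresponds to 4 points, so SD = 4/0.4 = 10 points. There are m = 80 residents per site, K = 8 or 12 sites, and a two-sided alpha of 0.05.

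**Assumptions.** Two strata of equal size (above and below the median), equal allocation within each, no loss to follow-up, and a t reference with between-site degrees of freedom. The ICC is the between-university share of variance *within* a size stratum.

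**The plan's own figure.** The 80% power cannot be reproduced without an ICC. Ignoring clustering, 99 residents per arm would suffice and 320 per arm gives 99.9% power, so a design effect must have been used. With SE² = (4/K)[ICC + (1 − ICC)/80] and t on K − 2 df, 80% power implies:
- K = 8: ICC 0.016, design effect 1 + 79 × 0.016 = 2.3
- K = 12: ICC 0.038, design effect 1 + 79 × 0.038 = 4.0

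A normal reference would imply 0.029 and 0.049. The t-based values are used below so that both scenarios start at the plan's stated power.

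**How far the standard error is overstated.** Let large and small sites differ by δ = 0.3 SD (3 points). This is an assumption.
- True variance of a site mean: 0.016 + 0.984/80 = 0.0283 (K = 8); 0.038 + 0.962/80 = 0.0500 (K = 12).
- Amount added to the residual variance when the stratum is omitted: K(δ²/4)/(K − 2). This is 8 × 0.0225/6 = 0.030 at K = 8 and 12 × 0.0225/10 = 0.027 at K = 12.
- Ratio of expected to true variance: 0.0583/0.0283 = 2.06 and 0.0770/0.0500 = 1.54. The SE is therefore overstated by factors of about 1.43 and 1.24.

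**Simulation of cluster means** (12,000 runs per setting, size-stratified 1:1 allocation):

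| Sites, ICC | Size gap (SD) | Power, no stratum | Power, with stratum | Type I error, no stratum |
|---|---|---|---|---|
| 8, 0.016 | 0 | 80% | 76% | – |
| 8, 0.016 | 0.1 | 77% | 77% | 4.4% |
| 8, 0.016 | 0.2 | 66% | 77% | 2.4% |
| 8, 0.016 | 0.3 | 50% | 77% | 1.0% |
| 12, 0.038 | 0 | 81% | 79% | – |
| 12, 0.038 | 0.1 | 79% | 80% | 4.8% |
| 12, 0.038 | 0.2 | 73% | 79% | 3.0% |
| 12, 0.038 | 0.3 | 64% | 80% | 1.9% |

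Repeat runs give 49–50% against 77–78% at 8 sites, and about 64% against 78–80% at 12, for the 0.3 SD gap. With the stratum in the model, type I error stays near 5%. The noncentral t gives 77% on 5 df and 79% on 9 df. Break-even is a gap of about 0.1 SD, or 1 point.

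**An optional prior-score covariate.** Let r be the assumed correlation between a university's prior mean and its 2019 mean. Power at ICC 0.05, when size is unrelated to score:

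| Sites | Current model | Prior mean only: r = 0.7 / 0.5 / 0 | Prior mean and stratum: r = 0.7 / 0.5 / 0 |
|---|---|---|---|
| 12 | 70–71% | 85% / 74–75% / 66% | 84% / 73% / 64% |
| 8 | 48% | 57% / 48% / 40% | 51% / 42% / 36% |

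These figures allow for chance correlation between the covariate and arm, which is considerable with few clusters. A formula that only removes r² of the site variance and subtracts one degree of freedom misses this and gives 65% at 8 sites for r = 0.7.

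**The case against.** The best defence is that a prespecified random-site model with a few resident-level covariates is a legitimate primary analysis when clusters are few. The random effect carries between-university variance into the standard error. The four covariates adjust for some differences in intake. Omitting the stratum makes the test conservative, not invalid, and each site-level term uses up a scarce degree of freedom.

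Much of this stands. The validity of the planned test is not in question, and the stratum does cost a little power if size is irrelevant. The 0.3 SD gap is also demanding: it alone adds 0.3²/4 = 0.0225 to the between-university variance, more than the within-stratum ICC of 0.016 used at 8 sites. With a 0.1 SD gap there is almost nothing to gain. But the loss from leaving the stratum out can be large, and the cost of putting it in is small.

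A reader might infer two stronger points that the documents do not support.

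- **That the trial discards each university's known prior exam performance and so loses power.** The sample size section says its assumptions rest partly on "actual scores obtained by all residents in Canada on the certification exams conducted in the spring of 2015 and the spring of 2016". It does not say that these scores are held by university. A design effect was calculated, which makes a breakdown plausible but does not establish it. The benefit also depends on an unknown correlation. At the 8-site minimum, the covariate gains about 9 points at r = 0.7, nothing at r = 0.5, and loses about 8 at r = 0.
- **That chance imbalance between universities biases the result.** Under cluster randomisation with a random site effect, such imbalance is imprecision already reflected in the interval.

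**Conclusion.** The point holds in a limited form. The plan stratifies on size, omits that stratum from the primary model, and claims balance on inequalities that size stratification does not control. The consequence is a possible loss of power and an over-wide confidence interval. It is neither bias nor inflated type I error.

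The size of the loss depends on how strongly size predicts score, which the documents do not say. It is negligible at a gap of about 0.1 SD. At 0.2 SD it is about 11 points of power at 8 sites and 6 at 12. At 0.3 SD it is about 27 and 16 points, with type I error of 1–2%. These figures assume ICCs back-solved from the stated 80% power, two equal strata, equal allocation within strata among the universities analysed, and a t reference. They also assume that resident covariates do not absorb the size effect; if they did so in part, the loss would be smaller. The ICC in the appendix should replace the assumed values before any power figure is relied on.

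The absence of a prior-score covariate is not a defect on this evidence.

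**What to change.** 1. Add the size stratum used in randomisation as a fixed effect in the primary mixed model.
2. Count it in the between-site degrees of freedom (K − 3 in place of K − 2: 5 at 8 sites, 9 at 12), and name the degrees-of-freedom method.
3. Reword the sentence in the allocation section so that it claims balance on university size only.

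The stratum is known from the randomisation, so no new data are needed. If size turns out to be unrelated to score, the cost is about 2–4 points of power at 8 sites and about 1 point at 12. The change should be fixed before any scores are released.

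Optionally, if written scores for 2015 and 2016 can be obtained by university, the team could check how well one year's university means predict the next. It could then decide in advance whether to add the prior mean as a covariate, given the number of sites. At 8 sites, having both terms roughly breaks even at r = 0.7 and loses power at lower correlations when size is unrelated to score. The prior mean should therefore not be added by default.
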